6.1.2 Dosing regimen for patients on Pasireotide in combination with cabergoline treatment

Cabergoline is in the form of 0.5mg tablet. Cabergoline should be taken according to guidelines in the parent protocol. It is usually taken after a full meal. As per the parent study, if monotherapy with pasireotide does not allow the patient to receive biochemical control, cabergoline can be added at a starting dose of 0.5mg once daily. If the patient does not achieve biochemical control with cabergoline 0.5mg once daily treatment, in combination with pasireotide, then the cabergoline dose can be escalated up to 1.0mg once daily.

Dostinex is a generic form of cabergoline and can be used in the trial. If Dostinex is not available in a participating country, a different type of generic form can be used. For storage conditions, please refer to cabergoline Package Insert and SmPC.

For specific study treatment dose modifications regarding cabergoline in the SOM230B2411 trial, please refer to (appendix 12).

Cabergoline is mainly recommended for patients with borderline or moderately increased plasma IGF-I levels (<1.5 X the upper limit of normal), even though it is sometimes effective (leading to normal IGF-I levels) in patients with high baseline IGF-1 levels. More recent studies suggest that cabergoline, a more selective dopamine-2 receptor agonist, may be effective in a larger percentage of patients by further lowering GH or IGF-1 levels. Doses vary from 0.3 to 7

mg/wk (one to seven administrations per week). The maximum suppression of GH has been achieved from 0.5 mg daily to 1 mg twice weekly.

6.1.3 Dosing regimen for patients on Pasireotide in combination with another treatment for Cushing's Disease or Acromegaly

Please follow all dosing guidelines outlined in the parent protocol for patients on any combination treatments.

6.1.4 Ancillary treatments

Not applicable

6.1.5 Rescue medication

Not applicable

6.1.6 Guidelines for continuation of treatment

Not applicable

6.1.7 Treatment duration

Patients will continue to receive pasireotide alone or in combination with another treatment for Cushing's Disease and Acromegaly, as long as they continue to derive benefit as per Investigator assessment, the drug becomes commercially available in their country, or until one of the discontinuation criteria is met (please refer to [Section 7.1.5](#)). At every visit, the investigator is required to confirm that the patient continues to have clinical benefit and may continue receiving study treatment. A patient will reach the end of the roll-over study when pasireotide treatment is permanently discontinued.

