2.1 Study rationale and purpose

The purpose of this rollover study is to evaluate long term safety data and allow continued supply of pasireotide (s.c. and/or LAR) to patients who are currently receiving treatment in a Novartis-sponsored trial and have fulfilled all required assessments in the parent study, are benefiting from the treatment as judged by the investigator and are unable to access pasireotide treatment outside of a clinical study. Parent studies eligible to participate in the roll-over study will be decided by Recordati. Investigator initiated trials (IITs) will not be included. The patient must have fulfilled all required assessments in the parent study and the parent study must be in the process of being completed or terminated and reported.

Patients will continue to receive pasireotide alone or in combination with another treatment for Cushing's Disease and Acromegaly, as long as they continue to benefit as per Investigator assessment, or until one of the discontinuation criteria is met (please refer to [Section 7.1.5](#)).

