Pasireotide is currently approved for use in Cushing's disease (s.c. formulation) in over 80 countries, and for use in acromegaly (i.m. LAR formulation) in over 30 countries worldwide. The safety profile of both formulations of pasireotide has been well characterized in a comprehensive development program and is similar to the established profile of SSAs, except for the higher incidence and magnitude of hyperglycemia, which is manageable with proper treatment with anti-diabetic medication. The mechanism of the pasireotide-induced hyperglycemia has been well characterized in mechanistic studies. It is primarily a consequence of decreased secretion of insulin and incretins, with no change in hepatic or peripheral insulin

sensitivity, is less severe in responders than non-responders, and is reversible upon discontinuation. The risk of hyperglycemia is minimized by monitoring of patients' FPG and HbA1c levels and appropriate management. Additional expected pharmacodynamic effects of pasireotide are well known and are primarily GI disturbances, bradycardia, mild QT prolongations, cholelithiasis and transient elevations in serum levels of transaminases. These effects can be effectively monitored and managed, as detailed in the IB and in the label. No unexpected new findings have emerged with long-term exposure to pasireotide.

Overall, pasireotide has a favorable benefit/risk profile in the discussed indications. Patients rolled-over to this study are those who have benefited from the treatment with pasireotide and continue to obtain this benefit with continuation of the treatment. The current label and IB fully characterize both efficacy and safety aspects of pasireotide, s.c. and LAR, to enable its appropriate use to maximize benefit while minimizing risks to patients. The risk to patients in this trial may be minimized by compliance with the eligibility criteria and study procedures, and close clinical monitoring. There may be unforeseen risks with pasireotide which could be serious.

3 Objectives and endpoints

Objectives and related endpoints are described in [Table 3-1](#) below.

Table 3-1 Objectives and related endpoints

Objective	Endpoint	Analysis
Primary		
To evaluate long term safety data i.e. SAEs and AEs	Frequency and severity of AEs/SAEs	Refer to Section 10.4
Secondary		

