4.3 Definition of end of the study

End of study is defined as either 10 years from FPFV (or until 10-Jun-2023 in the UK) or when all patients on this study have permanently discontinued pasireotide treatment or have been able to obtain commercial supply according to local regulations or have been able to receive the drug through country-specific programmes outside of this clinical trial (applicable to Brazil, France, Germany, India, Italy, Malaysia, Mexico, Peru and Thailand) and the end of treatment visit and all safety follow-up procedures have been performed for each patient, whichever comes first.

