5.2 Inclusion criteria

Patients eligible for inclusion in this study have to meet **all** of the following criteria:

1. Patient is currently participating in a Novartis-sponsored study receiving pasireotide (LAR and/or s.c.) on monotherapy or combination therapy (for Cushing's Disease or Acromegaly), and has fulfilled all required assessments in the parent study and patients that are benefiting from the study treatment have no other alternatives.
2. Patient is currently benefiting from the treatment with pasireotide, as determined by the investigator
3. Patient has demonstrated compliance, as assessed by the investigator, with the parent study requirements.
4. Willingness and ability to comply with scheduled visits, treatment plans and any other study procedures.
5. Written informed consent obtained prior to enrolling in roll-over study and receiving study medication.
 - If consent cannot be expressed in writing, it must be formally documented and witnessed, ideally via an independent trusted witness.

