7.1.5.1 Criteria for premature patient withdrawal

Patients may voluntarily withdraw from the study or be dropped from it at the discretion of the investigator at any time. Patients may be withdrawn from the study if any of the following occur:

- Death.
- Lost to follow-up.
- Staying in the study would be harmful.
- Patient/guardian decision.
- Physician decision.
- Non-compliance to protocol requirements.
- Protocol deviation.
- Pregnancy.
- Study terminated by sponsor.
- Study treatment has become available through country-specific programmes outside of this clinical trial (applicable to Brazil, France, Germany, India, Italy, Malaysia, Mexico, Peru and Thailand).

Study treatment has become commercially available and reimbursed (when current treatment becomes commercially available and reimbursed in that indication, the patient will have to be withdrawn from the study and will have completed the study as per protocol).

In addition to the general withdrawal criteria, the following criteria may also require study treatment discontinuation:

If any of the criteria below are met during routine examinations that are part of standard of care, study medication should be discontinued immediately. Re-challenge of study medication is prohibited once discontinuation criteria are met.

Hepatic-related discontinuation criteria

- Jaundice or other signs of clinically significant liver dysfunction
- ALT or AST $> 3 \times$ ULN and Total Bilirubin $\geq 2 \times$ ULN and ALP $< 2 \times$ ULN
- ALT or AST $> 5 \times$ ULN and $\leq 8 \times$ ULN persistent for more than 2 weeks
- ALT or AST $> 8 \times$ ULN

QT related discontinuation criteria

- Confirmed QTcF >500 ms and discontinuation recommended by a cardiologist
- QTcF > 480 msec, if the investigator determines it is no longer safe for the patient to continue in the study, based on ECGs, cardiac examination and recommendation from a cardiologist.
- Clinically significant arrhythmias including:
 1. Any ventricular or supra-ventricular tachyarrhythmia associated with symptoms of hemodynamic compromise.
 2. Sustained ventricular tachycardia (>30 s) irrespective of symptoms.
 3. Recurrent non-sustained VT (≥ 3 beats) during any 24-hour monitoring period.
 4. Clinically significant brady-arrhythmia or third degree AV block.
 5. Need to use a drug with known risk of TdP.

Hyperglycemia related discontinuation criteria

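### Protocol 6.1.7 ends study treatment once the drug is on the market in the country, but 7.1.5.1 requires withdrawal only if it is also reimbursed in the patient's indication

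*Protocol*

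**What the plan says.** **Leaving the study.** Protocol 6.1.7 (Treatment duration) gives three items in one sentence: continuing benefit as judged by the investigator; "the drug becomes commercially available in their country"; "or until one of the discontinuation criteria is met", with a reference to Section 7.1.5.

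Protocol 7.1.5.1 opens its list with "Patients may be withdrawn from the study if any of the following occur". Its item on commercial access is stricter in force and narrower in scope: "when current treatment becomes commercially available and reimbursed in that indication, the patient will have to be withdrawn from the study". The same list adds country-specific programmes in nine named countries.

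The protocol summary (Study design), 2.1 and 4.1 also say how long treatment continues. Each names loss of benefit and the discontinuation criteria, and none has a separate availability clause.

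**Entering the study.** Section 2.1 describes the intended patients as those who, among other things, "are unable to access pasireotide treatment outside of a clinical study". Inclusion criterion 1 in 5.2 ends with a different phrase: "patients that are benefiting from the study treatment have no other alternatives".

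**The concern.** The primary objective is long-term safety, so the rule that stops treatment also largely determines how long each patient is observed. If two sections give different stopping conditions, two sites can treat identical patients differently and each can point to the protocol.

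Two things are at stake. For the data, the date of last dose fixes the end of the on-treatment period (Protocol 10.5.3.1; SAP 4.1) and the duration of exposure (SAP 7.3), and the stop enters the disposition table (SAP 4.2.1). The difference would follow country and indication, and indication is one of the SAP's reporting groups. For patients, a literal use of 6.1.7 could end supply to someone for whom the drug is on sale locally but not reimbursed, or not for their disease.

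**Working it through.** No arithmetic decides this point. The check is to set the exit clauses side by side and run patients through them.

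**Step 1: is the 6.1.7 clause a separate trigger?** The sentence is badly built. It begins with a condition for continuing and then inserts an event. The only workable reading is that treatment continues until the drug is on the market. The next item, "or until one of the discontinuation criteria is met", starts with a disjunction, so as worded the availability clause stands beside the 7.1.5 criteria and does not abbreviate them.

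**Step 2: compare the conditions.**

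| Condition | 6.1.7 availability clause | 7.1.5.1 commercial-access item |
|---|---|---|
| On the market | yes, in the country | yes |
| Reimbursed | not required | required |
| In the patient's indication | not required | required |

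**Step 3: run the cases.**

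| Patient's situation | 6.1.7 clause | 7.1.5.1 commercial-access item |
|---|---|---|
| 1. Marketed, not reimbursed | ends | not met |
| 2. Marketed and reimbursed, but only for another indication | ends | not met |
| 3. Marketed and reimbursed in the patient's indication | ends | met, withdrawal required |
| 4. Not marketed, but a programme is open in one of the nine countries | not met; reached only through the reference to 7.1.5 | not met; the separate programme item lists it as a ground for withdrawal |

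The sections agree in case 3 and can be read together in case 4. They disagree in cases 1 and 2.

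**Step 4: can cases 1 and 2 arise?** The documents give good reason to think so.

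- Section 2.6 reports approval by disease and formulation: pasireotide is "approved for use in Cushing's disease (s.c. formulation) in over 80 countries", and the LAR form is approved for acromegaly in over 30.
- The parent studies in SAP Tables 2-1 and 2-2 also cover dumping syndrome, neuroendocrine tumours, melanoma and prostate cancer, all grouped as other diseases.
- Protocol 6.1.1 and 6.5.1 allow local commercial product as study supply, so participants are expected in places where the drug is sold.

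**Step 5: what does the difference do to one patient?** Let g be the number of days between the stop under 6.1.7 and the later stop for another reason. The on-treatment period runs to 84 days after the last LAR dose or 30 days after the last s.c. dose. These offsets are the same under either rule, so that period shortens by about g days. For LAR, dosed every 28 days, a gap of g = 84 days (chosen only for illustration) means 84 / 28 = 3 injections. The documents do not give g for any patient.

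**Step 6: how many patients?** This cannot be computed. No counts by country, indication and reimbursement status are given.

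**Step 7: entry.** Take a patient who cannot get pasireotide elsewhere but has another therapy open to them. The patient fits 2.1. Under criterion 1 the answer depends on whether the alternatives meant are other ways to obtain pasireotide or other treatments for the disease. Sections 1.1.1 and 1.1.3 describe other treatments for Cushing's disease and neuroendocrine tumours, so the two readings can give different answers. The text does not say which is meant.

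**The case against.** The best defence is that 6.1.7 is loose shorthand for 7.1.5.1. Its sentence is ungrammatical, imposes no duty to withdraw and refers to 7.1.5, while the explicit mandatory rule is in 7.1.5.1. The summary, 2.1 and 4.1 have no bare availability clause. The Amendment 5 rationale mentions market availability and reimbursement together. Commercial product is allowed as study supply, which would be odd if marketing alone ended participation. This may well describe the intent. It does not remove the conflict, because 6.1.7 is the section a site consults on treatment duration and it words availability as an item of its own.

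At entry, the defence is that criterion 1, read beside 2.1 in a continued-access study, naturally means no other way to continue pasireotide. The broad reading would bar many patients, yet the Amendment 2 text records 301 enrolled. That has force. The entry point is therefore unclear wording and not a demonstrated contradiction.

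The defence also notes that the study is descriptive, with no hypothesis and no sample size calculation, and that nothing shows a site having stopped treatment under 6.1.7. Both statements are correct. They limit the consequences without resolving the text.

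**Conclusion.** The exit conflict stands. The same patient is ended under 6.1.7 and does not meet the availability criterion of 7.1.5.1 whenever pasireotide is marketed without reimbursement or only for another indication. This rests on reading the garbled 6.1.7 sentence as an end to treatment, which is its only workable sense. It affects last dose, exposure, length of safety follow-up and continued access. It affects no test or sample size. The differing entry wording is a lesser, secondary point.

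Four stronger inferences are tempting, and the documents do not support them.

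- *That 4.3 is a further patient-level test.* Its phrase, "have been able to obtain commercial supply according to local regulations", belongs to the definition of the end of the whole study, as does the matching text in 7.1.3. Neither tells a site to withdraw a patient.
- *That a patient with reimbursed access could be eligible and due for withdrawal on day 1.* This needs the protocol summary to decide eligibility. Sections 5.1 and 5.2 require every listed criterion. The summary is abridged: it also omits inclusion criteria 4 and 5 and the pregnancy and contraception exclusions. Such a patient falls outside 2.1 and has an alternative under criterion 1.
- *That SAP deviation coding depends on which section is followed.* The SAP 8.1 term for other withdrawal criteria that were met uses the wording of the 7.1.5.1 heading, so it points to that section.
- *That a number of affected patients can be estimated.* The 259 ongoing patients are a count from Amendment 2, dated September 2017, and any share applied to them would be invented. The country figures in 2.6 are worldwide approvals. They are not counts of participating countries or of reimbursement.

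**What to change.** Reconcile 6.1.7 with 7.1.5.1 so that a single availability condition appears in the same words in both, with explicit terms for reimbursement and indication. Reconcile inclusion criterion 1 with 2.1 so that the reader knows whether alternatives means other routes to pasireotide or other treatments. The sponsor decides which condition applies in each case; this review does not choose one.

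The cost is a wording amendment to one pair of clauses on exit and one pair on entry, with the approvals that Protocol 12.1 requires for any change. It needs no new data, visits or analyses. Section 4.3 and the SAP deviation list need no change on this account.

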6.2 Dose modification guidelines

The starting dose of pasireotide alone or in combination with another treatment for Cushing's Disease and Acromegaly, should be the same dose as that which the patient was receiving in the parent study at roll over. Changes to pasireotide, and any medication given in combination with pasireotide dose, will be based on the investigator's judgment.

Please refer to [Appendix 2](#) through [Appendix 12](#) (Section 14.2 through Section 14.12) for dose modification guidelines.

6.2.1 Starting dose rationale

The starting dose of pasireotide alone or in combination with another treatment for Cushing's Disease and Acromegaly, should be the same as that which the patient was receiving in the parent study at the roll over.

6.3 Concomitant medications

6.3.1 Prohibited concomitant therapy

The use of concomitant medication with known risk of Torsades de pointes (TdP) is prohibited. In case a patient needs to take a medication with known risk of TdP, it will require study drug discontinuation prior to starting the medication. Please see [Appendix 1](#) for further guidance on QT prolonging medication.

Medications with a potential risk of TdP should be avoided whenever possible.

Refer to [Appendix 1](#) for guidance regarding medications which pose a known risk for QT prolongation.

6.4 Patient numbering, treatment assignment or randomization

6.4.1 Patient numbering

Each patient is identified in the study by a Subject Number (Subject No.), that is assigned when the patient is enrolled in the roll over study and is retained as the primary identifier for the patient throughout his/her entire participation in the trial. The Subject No. consists of the Center Number (Center No.) (as assigned by Recordati to the investigative site) with a sequential patient number suffixed to it, so that each subject is numbered uniquely across the entire database. Upon signing the informed consent form, the patient is assigned to the next sequential Subject No. available to the investigator through the Oracle Clinical Remote Data Capture interface. Additionally, an e-CRF will be completed that identifies the patient by gender and data of birth and previous study, site/center and subject number.

6.4.2 Treatment assignment or randomization

Not applicable

6.4.3 Treatment blinding

Not applicable

6.5 Study drug preparation and dispensation

All dosage prescribed to the patient and all dose changes during the study must be recorded on the Dosage Administration Record CRF.

Investigator staff will identify the study treatment package(s) to dispense to the patient. Investigator staff will add the patient number on the label. For global supply the study medication packaging has a 2-part label. Immediately before dispensing the package, Investigator staff will detach the outer part of the label from the packaging and affix it to the source document (Drug Label Form) for that patient's unique patient number.

6.5.1 Study treatment packaging and labeling

Pasireotide for the roll-over study can be provided where appropriate as local commercial material or as global clinical study supply (Open label), packed and labeled under the

responsibility of the Sponsor's Clinical Supply. Study treatment labels will be in the local language and comply with the legal requirements of each country. They will include storage conditions for the drug but no information about the patient.

Combination treatments should be labeled and supplied in accordance with the parent protocol. When available, commercial treatment should be used as a first option.

Table 6-2 Packaging and labeling

Study treatments	Packaging	Labeling (and dosing frequency)
Pasireotide s.c. (0.3mg, 0.6mg and 0.9mg)	Solution for subcutaneous injection in ampoule	Labeled as 'SOM230' (b.i.d. or t.i.d)
Pasireotide LAR (10mg, 20mg, 40mg and 60mg)	Microparticle powder for suspension in vial	Labeled as 'SOM230 LAR' (q28d)
	Solution for suspension (vehicle) in ampoule	Labeled as 'solvent' (q28d)

6.5.2 Drug supply and storage

Study treatments must be received by designated personnel at the study site, handled and stored safely and properly, and kept in a secured location to which only the investigator and designated site personnel have access. Upon receipt, pasireotide alone or in combination with another treatment for Cushing's Disease and Acromegaly, should be stored according to the instructions specified on the drug labels and in the [Investigator's Brochure]. For patients receiving pasireotide s.c., a 3-month supply of pasireotide can be dispensed to the patient. Patients receiving pasireotide LAR, must return monthly to the participating site to receive their injections. During these visits, limited drug dispensing information will be collected and reported within the drug accountability log.

Table 6-3 Supply and storage of study treatments

Study treatments	Supply	Storage
Pasireotide s.c.	local commercial material or global clinical study supply (open label) supplied by Sponsor	Refer to study treatment label
Pasireotide LAR	local commercial material or global clinical study supply (open label) supplied by Sponsor	Refer to study treatment label
Combination treatments	Should be supplied in accordance with the parent protocol. Where available, commercial treatment should be used as a first option.	Refer to study treatment label

